4.3 Treatment Assignment

An interactive web response system (IWRS) will be used for randomisation to a treatment arm and assignment of blinded investigational product kit numbers. A subject is considered randomised into the study when the investigator/designee notifies the IWRS that the subject meets eligibility criteria and the IWRS allocates the assignment of a blinded investigational product number to the subject. An interactive voice response system (IVRS) will also be available as a back-up.

Subjects will be randomised at a 2:1 ratio to receive either CAM-3001 or placebo.

The procedure for using IWRS/IVRS is as follows:

- The investigator or designee confirms that written informed consent has been obtained and that the subject meets all eligibility criteria.
- The unblinded investigational product manager will log onto the IWRS/IVRS to obtain the treatment allocation on the day indicated by the investigator/designee.
- The IWRS/IVRS assigns a treatment arm (CAM-3001 or placebo) and investigational product number(s) to the subject and then sends a confirmatory fax or e-mail with the subject identification number and investigational product number(s) is sent to the unblinded investigational product manager.

Investigational product (CAM-3001 or placebo) must be administered as soon as possible after receipt of the investigational product number. If there is a delay in the administration of investigational product such that it will not be administered on the day of receipt of the investigational product number, the MedImmune study monitor and/or its designee must be notified immediately.

4.4 Blinding

This is a double-blind study. Since CAM-3001 and placebo are not identical in appearance/viscosity, investigational product will be handled by an unblinded investigational pharmacist at the site and will be administered by an unblinded study team member who will not be involved in the management of study subjects. An independent investigational product monitor will also be unblinded to perform investigational product accountability. Neither the subject nor any of the investigator or sponsor staff who are involved in the treatment or clinical evaluation of the subjects will be aware of the treatment received (International Conference on Harmonisation [ICH] E9).

The vendor for packaging and labelling of the clinical supplies, designated IWRS/IVRS personnel and designated MedImmune Clinical Research Pharmacy Service (CRPS) personnel will have access to information that may identify a subject's treatment allocation. At site, an independent monitor, who will only review the pharmacy records, and the investigational product manager are the only individuals who will have access to information that identifies a subject's treatment allocation. These individuals must not reveal randomisation or treatment information to anyone or participate in or be associated with the evaluation of study subjects. In the event that the treatment allocation for a subject becomes known to the investigator or other study staff or needs to be known to treat an individual subject for an AE, the sponsor must be notified *immediately* by the investigator.

Protocol MI-CP219; Amendment 3 Final

To prevent potential unblinding at site because of observed efficacy or laboratory changes, a "dual assessor" approach will be used to evaluate efficacy and safety. A Joint Count Assessor is a skilled arthritis assessor and will be responsible for completing the joint counts only. The Safety Assessor should be a rheumatologist and will have access to both safety and efficacy data. The Safety Assessor will have access to source documents, laboratory results, and electronic case report forms (eCRFs) and be responsible for making treatment decisions based on a patient's clinical response and laboratory parameters. The Safety Assessor will not complete the joint count assessments.

In the case of a medical emergency, where the treatment received by the subject needs to be identified to appropriately treat the subject or manage their condition, the sponsor should be notified immediately and prior to unblinding whenever possible. The investigator will have the ability to unblind the subject treatment in case of such an emergency. Any unblinding due to an emergent safety issue will be performed according to the IWRS/IVRS manual. The investigator will also document and report the action to the sponsor without revealing the treatment given to the subject.

The primary statistical analysis of the primary efficacy endpoint and other endpoints at Day 85 will be performed when the last subject recruited outside of Japan has completed all assessments at Day 85. MedImmune will be unblinded at the primary analysis excluding subjects enrolled in Japanese sites. The purpose of this analysis is for internal decision making on the progression of the clinical programme, so this analysis will not impact the conduct of the current study. This is the final analysis of the primary efficacy endpoint, so no alpha adjustment for analysis will be made. The analysis methodology and the review of the resulting data by the sponsor will be described in the Statistical Analysis Plan (SAP). The treatment assignment of the Japanese subjects will remain blinded at the primary analysis.

Investigational product will be supplied to the site as individually numbered CAM-3001 or placebo vials. The vials will be packaged into cartons and each carton will be labelled with a unique number range that corresponds to the labelled number series of the vials within the carton. Detailed instructions are in the Investigational Product Manual supplied by MedImmune.

4.5.1 Investigational Product (CAM-3001 and Placebo)

Investigational product will be distributed to clinical sites using designated distribution centres. The sponsor will provide the investigator(s)/designee with adequate quantities of investigational product. Vials are to be stored at 2-8°C at which temperature the product is viable until its listed expiry date on the IWRS/IVRS. Detailed instructions on the preparation of the investigational product, investigational product supply, dose preparation, and accountability will be provided in the Investigational Product Manual supplied by MedImmune/delegate.

Information in this manual will be specific for the unblinded product manager who will manage the preparation of the syringes for the study.

- **CAM-3001:** CAM-3001 is to be provided as a 1.15 mL fill in 2 mL vials. This fill volume was selected to allow volumes of 1 mL (100 mg) to be extracted. The active ingredient is formulated at a concentration of 100 mg/mL in a liquid formulation
- Placebo:
 Placebo will be supplied as 10.3 mL in 10 mL vials. This fill volume was selected to allow volumes of 10 mL to be extracted. Subjects randomised to the placebo group will receive 1 mL placebo per dosing. The placebo formulation is identical to the drug product with the exception of the active ingredient:

Vials are to be labelled in accordance with local regulatory requirements.

Specific details regarding investigational product supplies, dose preparation, and accountability will be provided in the Investigational Product Manual supplied to the sites.

The investigator's or site's designated investigational pharmacist is required to maintain accurate investigational product accountability records. Upon completion of the study, copies of investigational product accountability records will be returned to the sponsor or designee. All unused investigational product will be returned to a MedImmune-authorised depot or disposed of upon authorisation by MedImmune or authorised representative (refer to the

MedImmuneProtocol MI-CP219; Amendment 3CAM-3001FinalInvestigational Product Manual or other written instructions provided by MedImmune or itsdesignee for contact information and specific shipping instructions).

4.5.2 Treatment Regimens

A total of 264 subjects are required to be randomised into this study (216 subjects outside of Japan and 48 subjects in Japan); in order that at least 216 evaluable subjects (180 plus 36 evaluable subjects from Japan) complete the study to Day 85. Table 4.5.2-1 includes the treatment regimens for the study.

Fable 4.5.2-1	Treatment Regimens

Dose Cohort	Ν	Treatment
1	54	CAM-3001 10 mg (N = 36) or placebo (N = 18) SC every
1(Japan)	12	other week (total 7 doses) CAM-3001 10 mg (N = 8) or placebo (N = 4)
2	54	CAM-3001 30 mg (N = 38) or placebo (N = 18) SC every
2(Japan)	12	other week (total 7 doses) CAM-3001 30 mg (N = 8) or placebo (N = 4)
3	54	CAM-3001 50 mg (N = 36) or placebo (N = 18) SC every
3(Japan)	12	other week (total 7 doses) CAM-3001 50 mg (N = 8) or placebo (N = 4)
4	54	CAM-3001 100 mg (N = 36) or placebo (N = 18) SC every
4(Japan)	12	other week (total 7 doses) CAM-3001 100 mg (N = 8) or placebo (N = 4)

SC=subcutaneous

*2:1 randomisation CAM-3001:Placebo

4.5.3 Investigational Product Preparation and Administration

The dose of investigational product for administration must be prepared by the investigator's or site's designated investigational product manager. Detailed instructions regarding investigational product preparation can be found in the Investigational Product Manual that will be provided to the investigator's or site's designated investigational pharmacist.

The day of receipt of the first dose of investigational product is considered Day 1. CAM-3001 or placebo should be dispensed by qualified personnel and will be administered as SC injections in the upper arm, thigh, or abdomen.

Protocol MI-CP219; Amendment 3 Final

CAM-3001 Final Severe hypersensitivity reactions have been reported with the administration of IV gammaglobulins and nearly all approved monoclonal antibodies. Similar reactions are reported to be much less common with SC injection of monoclonal antibodies. Before the investigational product administration, medications and supplies for the emergency management of investigational product hypersensitivity reactions should be available. See Section 6.4.3 and Appendix 1 for additional information.

4.5.4 Concomitant Medications and RA Treatment

MedImmune

A concomitant medication is any drug taken during the study including over the counter drugs, herbal supplements, vitamins and vaccines, given to the subject during the study. All concomitant medications, including any changes during the study, will be recorded on the eCRF.

Concomitant therapies taken for the long term treatment of pre-existing conditions may be continued during the study provided they are in accordance with the exclusion criteria. It is preferred that these medications be stabilised prior to entry and continued wherever practical without variation of dose or regimen during the study.

In addition to the investigational product, all subjects will receive methotrexate at a weekly dose of 7.5 to 25 mg/week (oral or parenteral). Eligible subjects will have received methotrexate by the same route for at least 12 weeks and at stable and tolerated doses for at least 4 weeks prior to Screening. In addition, subjects will be allowed to receive stable doses of NSAIDS and stable dose of oral corticosteroids (\leq 10 mg/day prednisolone or equivalent (see study reference manual) if the dose has been stable for at least 4 weeks prior to Screening.

As stated in the inclusion criteria, all subjects must receive \geq 5 mg/week folic acid during the study as a single or divided dose to minimise methotrexate toxicity.

4.5.4.1 Modification of Treatments for RA

All changes to the RA treatment and the reasons for change must be clearly documented in the eCRF.
MedImmune CAM-3001 **Methotrexate and Corticosteroids**

Changes in ongoing RA treatment or introduction of new therapies are not allowed during the study period (Screening until Day 85). This includes the dose of methotrexate, corticosteroids and NSAIDS. After the Day 85 study visit, where possible the doses of background medication should be kept as constant as possible up to completion of the safety follow-up period (Day 169). Modifications to background RA medication will be permitted for safety reasons such as adverse reactions due to these medications (eg, gastrointestinal adverse events), and infectious diseases.

Subjects who require a change to their RA therapies for reasons other than safety, such as for poor disease control or worsening of their RA between Day 1 and Day 85 may be discontinued from dosing upon review by the medical monitor, but will remain in the study and be followed-up for safety. All study assessments should be completed, unless consent is withdrawn.

The risk/benefit to the subject should be carefully assessed and consideration given to the timing of any necessary dose modification or introductions of new medications during the study period and should be discussed with the medical monitor where possible.

Injection of IA corticosteroids is discouraged, but a maximum of 2 IA injections of corticosteroids (dose up to 40 mg of triamcinolone or equivalent) are allowed as needed to control joint flares during the treatment period of the study. Treated joints will not be counted for tenderness and swelling for 12 weeks post injection.

Analgesics

Analgesics and NSAIDS should be maintained at a stable dose for the duration of the study. Subjects should refrain from taking the usual morning dose of analgesics on visit days until after all clinical assessments have been completed (see Table 5.2-1 for Frequency of Assessments).

Disallowed Medications

The following medications are prohibited during the treatment period of the study:

- Any investigational agent other than CAM-3001
- Alkylating agents, including cyclophosphamide

MedImmune

CAM-3001

- Biologic agents or non-biologic DMARDS other than methotrexate
- Immunoabsorption columns, plasmapheresis and IV immunoglobulin therapy
- Live or live-attenuated vaccines

Immunisation with any live or live attenuated vaccine (ie, measles, mumps, rubella and polio vaccine, Bacillus Calmette-Guérin (BCG), typhoid, yellow fever, cold adapted live influenza strain vaccine or any other vaccines not yet licensed but belonging to this category) is specifically excluded during the treatment period (Centers for Disease Control and Prevention, ACIP Recommendations, 1993).

Subjects who are eligible for yearly influenza vaccine or who require booster vaccinations for other diseases can receive vaccination with killed/toxoid vaccines consistent with normal clinical practice. The effect of CAM-3001 on vaccine response is not known.

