Evaluations	Up to -28	1	4	8	15	29	43	57	71	85	88 ±2	99 ±3	113 ±7	169/ Disc ±7
VISIT	Screen	1	2	3	4	5	6	7	8	9	10	11	12	13
Urine βHCG		Х			Х	Х	Х	Х	Х	Х				X
INVESTIGATIONAL PRODUCT ADMINISTRATION		X			X	X	X	X	X	X				
SAFETY ASSESSMENT														
Height	Х													
Weight	Х													Х
Vital signs	Х	Х	Х	Х	Х	Х	Х	Х	Х	Х	Х	Х	Х	Х
AE/SAE assessment	Х	Х	Х	Х	Х	Х	Х	Х	Х	Х	Х	Х	Х	Х
Record concomitant medications	Х	Х	Х	Х	Х	Х	Х	Х	Х	Х	Х	Х	X	Х
Clinical chemistry, haematology with differential, platelets	Х	X			X	X	X	X	X	X		Х	Х	Х
Urinalysis	Х	Х			Х	Х	Х	Х	Х	Х		Х	Х	Х
Modified Borg scale (subjects completed) and O ₂ saturation (pulse oximetry)	х	X			X	X	X	X	X	X		X	X	X
Pulmonary Function Tests	Х	Х				Х				Х				X
PK/Immunogenicity														
CAM-3001 serum concentration		X	Х	X	X	Х		X		Х	Х	Х	Х	Х
Anti-CAM-3001 antibodies		Х				Х		Х		Х		Х	Х	X
DISEASE ACTIVITY														
Swollen joint count (66 joints)	X	X		X	X	Х	Х	X	X	X		Х	Х	X
Tender joint count (68 joints)	Х	Х		Х	Х	Х	Х	Х	Х	Х		Х	X	X
Patient assessment of pain	X	Х		Х	Х	Х	Х	Х	Х	Х		Х	X	X
Patient's global assessment of disease activity	X	X		X	X	X	X	X	X	X		Х	X	X

Protocol MI-CP219; Amendment 3 Final

	Screen	Treatment Period (Study Days)									Follow-up (Study Days)			
Evaluations	Up to -28	1	4	8	15	29	43	57	71	85	88 ±2	99 ±3	113 ±7	169/ Disc ±7
VISIT	Screen	1	2	3	4	5	6	7	8	9	10	11	12	13
Physician's global assessment of disease activity	Х	Х		Х	Х	Х	Х	х	X	Х		Х	X	Х
HAQ-DI	X	Х		Х	Х	Х	Х	Х	Х	Х		Х	Х	Х
Rheumatoid factor, anti-CCP antibodies	X	Х		Х	Х	Х	Х	Х	Х	Х		X		Х
PATIENT REPORTED OUTCOMES														
SF-36		Х				Х				Х				
FACIT-Fatigue		Х			Х	Х		Х		Х			Х	Х
MOS-sleep scale		Х				Х				Х				
CORRELATIVE STUDIES														
Receptor occupancy		Х	Х	Х	Х	Х		Х		Х	Х	Х	Х	Х
Whole blood for mRNA and miRNA analysis		X	X	X	X	X		X		X	Х	Х	Х	X
Serum for exploratory biomarker analysis		Х		Х	Х	Х		X		Х	Х	Х	X	Х
DNA Sample (optional)		Х												

Table 5.2-1 **Schedule of Subject Evaluations**

(optional) $AE = adverse event; \beta HCG = \beta$ human chorionic gonadotrophin; CCP = cyclic citrullinated peptide; CMV = cytomegalovirus; DNA = deoxyribonucleic acid; EBV = Epstein-Barr virus; ECG = electrocardiogram; FACIT = functional assessment of chronic illness therapy; HAQ-DI = Health Assessments Quesionairre-Disability Index; miRNA = micro ribonucleic acid; mRNA = messenger ribonucleic acid; MOS = Medical Outcomes Study; $O_2 = oxygen$; PK = pharmacokinetics; TB = tuberculosis; SAE = serious adverse event; SF-36 = Short Form 36

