5.3.4 Disease Evaluation and Methods

A clinical evaluation of disease activity should be done as described in the Study Reference Manual. This evaluation will encompass DAS28 and ACR responses.

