5.3.4.1 DAS28

The DAS28(CRP) has been validated against radiographic progression and physical function (HAQ-DI) and the validation profile is similar to the DAS28 Erythrocyte Sedimentation Rate (ESR) (Wells et al, 2009). In this study both CRP and ESR will be collected. Subjects are required to have at least moderately active disease as defined by DAS28 \geq 3.2 at Screening and Day 1 in order to be included in this study. The investigator will calculate DAS28(CRP) for Screening and DAS28(ESR) for Day 1 to assess this criterion.

The DAS28 considers 28 of the 68 tender joint count (TJC) and 28 of the 66 swollen joint count (SJC), general health (GH) using patient assessment of disease activity using the numerical rating scale with 0 = best, 100 = worst, plus levels of CRP (mg/L) or ESR (mm/hour).

DAS28(CRP) values will be calculated as follows (Wells et al, 2009):

DAS28(CRP) = 0.56 * sqrt(TJC28) + 0.28 * sqrt(SJC28) + 0.014*GH + 0.36 ln(CRP+1) + 0.96

DAS28(ESR) values will be calculated as follows:

DAS28(ESR) = 0.56 * sqrt(TJC28) + 0.28 * sqrt(SJC28) + 0.70*ln(ESR) + 0.014*GH

DAS28 will be categorised using the EULAR response criteria:

Protocol MI-CP219; Amendment 3 Final

Baseline DAS Score	Level of Improvement from Baseline (Day 1)									
	> 1.2	\geq 0.6 to \leq 1.2	< 0.6							
< 3.2	Good response	Moderate response	No response							
\geq 3.2 to \leq 5.1	Moderate response	Moderate response	No response							
> 5.1	Moderate response	No response	No response							

Table 5.3.4.1-1DAS28 Improvement

DAS = Disease Activity Score

DAS28 defined remission is DAS28 of < 2.6. Low disease activity is < 3.2 and high disease activity is > 5.1.

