5.3.4.2 ACR20, ACR50, and ACR70 Responses

The core components of the ACR response criteria are:

- Swollen joint count (66 joints; see below for details)
- Tender joint count (68 joints)
- Physician global assessment of disease activity (0-10 visual analogue scale [VAS]; see below for details)
- Patient global assessment of disease activity (0-100 VAS; see below for details)
- Patient pain assessment (0-100 VAS; see below for details)
- Patient reported functional disability (HAQ-DI; see below for details)
- Acute phase reactant (CRP and ESR)

A subject has an ACR response if all of the following occur:

- An improvement in the swollen joint count (66 joints)
- An improvement in the tender joint count (68 joints)
- An improvement in at least 3 of the following 5 assessments:
 - Physician global assessment of disease activity
 - Patient global assessment of disease activity
 - Patient pain assessment
 - Patient reported functional disability using the HAQ-DI
 - CRP or ESR

MedImmune CAM-3001 Subjects will be considered to have had an ACR20, ACR50 or ACR70 response if at least a 20%, 50% or 70% improvement from Day 1 (respectively) was observed in the criteria specified above.

68 Joint Assessments

The 68 joints to be assessed for tenderness are: temporomandibular (n = 2), sternoclavicular (n = 2), acromioclavicular (n = 2), the 8 proximal interphalangeal joints of the fingers, the interphalangeal joints of the thumbs (n = 2), the 8 distal interphalangeal joints, the 10 metatarsophalangeal, the 10 metacarpophalangeal joints plus the wrists (n = 2), elbows (n = 2), shoulders (n = 2), hips (n = 2), ankle mortise and tarsus (n = 4), knees (n = 2), and toes (n = 10) (Felson et al, 1993).

The 66 joints assessed for swelling are the same as those assessed for tenderness, except the hip joints are not included.

In order to calculate the ACR and DAS28 responses, each of the 68 joints will be evaluated for tenderness and swelling. Standardised metrology training will be provided if necessary.

Physician Global Assessment of Disease Activity

The physician global scale is a 10 cm VAS that asks the safety assessor to rate their subject's level of disease activity due to RA **'TODAY'.** Higher scores on this scale indicate increased (worse) disease activity.

Patient Global Assessment of Disease Activity

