7.2.6 Immunogenicity

The immunogenicity population is defined as all subjects who receive at least one dose of CAM-3001 and for whom at least one serum sample for immunogenicity testing is available.

The safety and PK/PD/Immunogenicity will be presented on an as-treated basis. The analyses of disease activity endpoints as well as summaries of baseline and demographic characteristics will be presented on an as-randomised basis; ie, treatment classification will be made according to the initial randomisation regardless of whether subjects received an investigational product different from that to which they were randomised.

Last-observation-carried-forward imputation may be used in certain disease activity endpoint analyses. All other missing data will be treated as missing without data imputation.

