7.3.1 Primary Endpoint

7.3.1.1 Efficacy

The primary efficacy objective will assess DAS28 response rates of CAM-3001 treated subjects compared with subjects who received placebo on the day of last dose of investigational product (Day 85). According to the EULAR response criteria an improvement from baseline in DAS28 of more than 1.2 would be considered a good response in subjects experiencing low disease activity (baseline DAS28 < 3.2) and a moderate response in subjects experiencing medium-to-high disease activity (baseline DAS28 \geq 3.2). A responder will be defined as a subject experiencing a decrease of more than 1.2 from their baseline DAS28 score, on the day of last dose of investigational product (Day 85).

Evaluable subjects will be cross-classified in a two-by-two contingency table according to their combined treatment group (CAM-3001 or Placebo) and by their responder status (Yes or No). The DAS28 response rate at Day 85 between combined CAM-3001 and combined placebo treatment groups will be compared using a two-sided Fisher's exact test.

Following the above comparison between the combined CAM-3001 and combined placebo treatment groups, each applicable dose cohort and the combined placebo group will be compared. These comparisons at the dose cohort level are not powered and as such their results will be considered in an exploratory setting. There will also be no adjustment for multiplicity. A 95% confidence interval of difference in DAS28 response rate between CAM-3001 and placebo treatment groups will be computed for each dose cohort to estimate the effect size of each CAM-3001 dose level.

The DAS28 response rate at Day 29 between CAM-3001 and placebo will also be compared using a Fisher's exact test.

To check the sensitivity of the comparisons, all the above analyses will be repeated over the respective cohort groupings but in the more restrictive ATP population. Due to the definition of the ATP population no imputation of the DAS28 score is needed for these analyses.

MedImmune CAM-3001 **7.3.1.2 Safety**

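### A joint given a permitted rescue steroid injection leaves the Day 85 count but stays in the Day 1 count; if it is simply omitted, a joint still active is scored as improved

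*Protocol*

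**What the plan says.** Section 4.5.4.1 states "Injection of IA corticosteroids is discouraged, but a maximum of 2 IA injections of corticosteroids" (each up to 40 mg triamcinolone or equivalent) may be given for flares in the treatment period. It then adds "Treated joints will not be counted for tenderness and swelling for 12 weeks post injection".

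Response is measured from Day 1. Section 7.3.1.1 has "A responder will be defined as a subject experiencing a decrease of more than 1.2 from their baseline DAS28 score", assessed at Day 85. The DAS28(CRP) formula in Section 5.3.4.1 takes the raw 28-joint counts under a square root. Section 5.3.4.2 defines ACR response as "at least a 20%, 50% or 70% improvement from Day 1 (respectively) was observed in the criteria specified above", and those criteria include the 66- and 68-joint counts.

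None of these sections removes an injected joint from the Day 1 count, prorates the later count, or treats rescue as non-response. Section 7.3.2.1 only summarises rescue corticosteroid use descriptively.

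On missing data, the conventions at the end of Section 7.2.6 allow last observation carried forward (LOCF) in certain disease activity analyses and continue "All other missing data will be treated as missing without data imputation". Section 5.3.4 says the clinical evaluation "should be done as described in the Study Reference Manual"; that manual is not among the documents.

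**The concern.** The exclusion starts at the injection and looks only forward. A joint counted as tender and swollen at Day 1, injected for a flare and still active at Day 85 would appear in the first count and not in the second. The subtraction then credits the subject with one resolved joint, although that joint needed rescue and did not settle. A joint quiet at Day 1 that flared and was injected would have its worsening left out.

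Both the primary DAS28 responder endpoint and the two ACR joint-count criteria are exposed. A permitted injection is not in itself a protocol violation, so the subject can remain in the Evaluable Population (Section 7.2.4) used for the primary test. If placebo subjects are rescued more often, extra placebo responders would dilute the drug effect.

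**Working it through.** **The plan's own figure.** Section 7.4 assumes 10% against 30% response, two-sided alpha 0.05 and Fisher's exact test. Exact enumeration gives power 0.878 at 120:60 (stated 86%) and 0.936 at 144:72 (stated 92%). Both are within two points, so 0.878 is the reference below.

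**Coverage.** Twelve weeks is 84 days. An injection on Day 1 runs to Day 85 and one on Day 3 to Day 87. Essentially every treatment-period injection therefore blanks the joint at the primary assessment.

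**Effect on one subject's DAS28, joint omitted.** Let T and S be the Day 85 28-joint tender and swollen counts with the injected joint included, and k the number of injected joints that are still tender and swollen. The score falls by

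0.56 × (√T − √(T−k)) + 0.28 × (√S − √(S−k)).

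Prorating replaces T−k by (T−k) × 28/(28−k), and S−k likewise. The joint counts are illustrative.

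| T/S | Omitted, k=1 | Omitted, k=2 | Prorated, k=1 | Prorated, k=2 |
|---|---|---|---|---|
| 16/12 | 0.112 | 0.229 | 0.056 | 0.117 |
| 10/8 | 0.142 | 0.293 | 0.098 | 0.207 |
| 4/4 | 0.225 | 0.492 | 0.198 | 0.447 |

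For example, at 10/8 with k=1: 0.56 × (3.162 − 3) + 0.28 × (2.828 − 2.646) = 0.091 + 0.051 = 0.142. As a share of the 1.2 cut-off, omission is worth 9-19% for one joint and 19-41% for two.

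**Hidden new flare.** For a joint quiet at Day 1, the missed worsening is 0.56 × (√(T+k) − √T) + 0.28 × (√(S+k) − √S), with T and S now excluding the joint. It is 0.109 and 0.214 for one and two joints at 16/12, and 0.198 and 0.378 at 4/4.

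**A borderline subject (assumed values).** Day 1 with 8 tender and 8 swollen joints, patient global 60 and CRP 15 gives DAS28 5.17. Day 85 with 6 and 6 active, global 38 and CRP 8 gives 4.34, a fall of 0.83: non-responder. Leaving out two of those six as injected gives 3.96, a fall of 1.21: responder.

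**ACR joint counts.** Each omitted joint adds k divided by the baseline count: 1/20 = 5 percentage points, 1/10 = 10 points, 2/10 = 20 points. Two joints at a baseline of 10 meet the ACR20 requirement on that count alone; the other criteria must still be met.

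**Trial level.** The protocol gives neither an injection rate nor an SD. Assume that the SD of DAS28 change is 1.2 (range 1.0-1.5), that 10% of placebo subjects and no active subjects have one joint injected, that the joint is among the 28, active at Day 1 and still active at Day 85, and that counts are 10/8. A 10% placebo response fixes the mean fall at 1.2 − 1.2816 × SD. The share of injected placebo subjects who become responders is P(fall > 1.2 − 0.142) − 0.10 = 0.022 (0.027 at SD 1.0, 0.018 at SD 1.5). Expected extra responders: 60 × 0.10 × 0.022 = 0.13. Placebo response becomes 10.22%.

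| Scenario | Placebo | Active | Power, 120:60 |
|---|---|---|---|
| No effect | 10.00% | 30.00% | 0.878 |
| 10% of placebo injected, none on active | 10.22% | 30.00% | 0.868 (0.866-0.870 over the SD range) |
| Same, injected subjects improve 0.5 less | 10.12% | 30.00% | 0.873 |
| 10% of placebo, 5% of active | 10.22% | 30.21% | 0.875 |
| 10% in both arms | 10.22% | 30.42% | 0.881 |

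**The case against.** The strongest reply is that the sentence tells the assessor not to count the joint but does not say how an uncounted joint enters the score. It could be omitted, prorated or treated as missing, and the Study Reference Manual or an analysis plan may settle this. That is fair as to the reading. It does not remove the point: the exclusion itself is a stated rule, and the formula it feeds uses raw counts.

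The reply goes further on the missing-data reading, and there it stands. A reader might infer that every reading of the sentence is biased. The documents do not support that. Section 7.2.6 names LOCF. Section 7.3.1.1 says the according-to-protocol repeat needs no imputation, which implies that the Evaluable analysis may use it. Section 7.3.2.1 drops imputation for DAS28 time points other than Days 29 and 85. If an uncounted joint made the score missing and LOCF were applied, an earlier score would be carried to Day 85 and the bias would largely disappear.

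It is also fair that a joint the steroid has settled is unaffected, that a joint outside the 28 cannot move DAS28, and that the primary comparison is repeated in the according-to-protocol population (Section 7.2.3). That repeat is only partial cover: a permitted injection is not on its face a medication violation, so these subjects need not be excluded from it.

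**Conclusion.** The point holds as a minor one. On the plain reading, omission from the raw count credits a rescued joint that is still active as improvement, by 0.11-0.23 DAS28 units for one joint and 0.23-0.49 for two, and hides a new flare. Prorating reduces the error without removing it. Missing with LOCF largely avoids it.

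The effect on the treatment comparison is small. Only rescued subjects near the 1.2 cut-off or near an ACR joint-count threshold can change status, and power moves by about one point (0.878 to 0.868) under the assumed 10% one-sided injection rate. That is still above the stated 86%.

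Two stronger inferences are not supported. A reader might suppose a large power loss: with rescue in 10% of placebo and 5% of active non-responders, power falls to 0.798 or 0.707 if 25% or 50% of them become responders. The DAS28 shift gives only about 2% for one joint and about 5% for two (shift 0.293, SD 1.2), and the documents contain nothing to support higher rates. A reader might also fear a false positive. If placebo is rescued more often, the error runs towards no difference. The real injection rate in each arm remains unknown.

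**What to change.** Replace the counting sentence in Section 4.5.4.1 with: *An injected joint is scored for 12 weeks at its tender/swollen status recorded at the time of injection (or at the last visit, if worse).* Apply it to both DAS28 and ACR. Using the status at injection matters because freezing the joint at the previous visit alone could miss a flare that began between visits. Record the joint, date and status on the eCRF. Add a sensitivity analysis of the primary endpoint counting every subject injected before Day 85 as a non-responder.

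The cost is one sentence, a small eCRF addition and one extra analysis. Section 4.5.4.1 already requires RA treatment changes to be documented. Table 5.2-1 already schedules joint counts on Days 1, 8, 15 and every 14 days to Day 85, so no scheduled visit is added. The drawback is a conservative score where the steroid truly resolved the joint: DAS28 would be 0.11-0.49 higher than a direct count, with slightly lower response rates.
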